- Evaluate all masked exams. *Even though only the first masked exam where failure criteria is met is relevant to the primary outcome, save stereoacuity failure criteria flag in a masked-exam-level dataset because interested in whether this criteria is met at the 3 year visit also, and may also be interested in other visits as well.*
- 250
- 251
- 252
- Determine the best stereoacuity at the baseline visit. Note that stereo was to be retested unless the patient scored 40 arcsec on the initial test.
- 253
- 254
- Compare masked exam initial to best baseline stereo and determine whether meets criteria for 2 or more level worsening (use Table 1 under step 1).
- 255
- 256
- If the worsening was not confirmed by the retest or the retest was not completed, the patient was considered not to have met stereoacuity failure criteria.
- 257
- 258
- 259
6. Determine whether patient was reoperated or underwent treatment with botulinum toxin
- 260
- Get treatment used records from all visits, regardless of whether a masked exam was completed
- 261
- 262
- If REOPERATION = 1 for any treatment used, and set patient-level reoperation to 1 and capture reoperation date
- 263
- 264
- 265
7. Calculate surgical failure at patient level and set timing variable for survival analysis (time to failure or censoring time)
- 266
- Loop through masked exam records for each patient and determine the first masked exam at which any of the three objective failure criteria were met.
- 267
- 268
- In patient-level dataset:
 - If reoperation occurs and surgical failure has not been met (either not at all or not by the time of reoperation), failure = 1 and failure time = months between surgery and reoperation
 - If one of the surgical failure criteria were met, either before reoperation or in a patient who is not reoperated, failure = 1 and failure time is based on visit type (e.g. 6 months, 12 months, etc.) or months between failure and surgery if failure occurs at an unspecified visit
 - If patient does not meet surgical failure and is not reoperated, failure = 0 and failure time is based on type of last completed visit (e.g. 6 months, 12 months, etc.)
- 269
- 270
- 271
- 272
- 273
- 274
- 275
- 276
- 277
- 278
- 279
- 280
8. Get cumulative probability of surgical failure by 3 years for each treatment group – from Kaplan-Meier survival analysis
- 281
- 282

- 283 • Run Kaplan-Meier survival analysis using proc lifetest, and specifying the method as
- 284 Kaplan-Meier.
- 285 • Output survival probabilities and confidence intervals to a dataset
- 286 • Create failure estimates and confidence intervals

```

287
288 /*****
289     PERFORM K-M ANALYSIS
290     PRIMARY OUTCOME
291     CUMULATIVE PROBABILITY OF SURGICAL FAILURE
292     NOTES FOR K-M SURVIVAL ANALYSIS
293     NUMBER AT RISK = NUMBER AT RISK GOING INTO THE VISIT
294                     (E.G. LAST PERSON AT 3 MONTHS BEFORE 6 MONTHS)
295     OUTSURV OPTION IN PROC LIFETEST STATEMENT CREATES AN OUTPUT DATASET
296     THAT CONTAINS SURVIVAL ESTIMATES AND CONFIDENCE LIMITS.
297     PARENTHETICAL IN TIME STATEMENT INDICATES WHAT CENSORING VALUE IS
298 *****/
299
300 %sort (roster, trtgroup);
301 proc lifetest data = roster method=km  outsurv=failresults plots=none alpha=.05;
302     time failtime*fail(0);
303     by trtgroup;
304     title2 'K-M Survival Analysis for Surgical Failure';
305 run;
306
307 proc print data = failresults;
308     title2'Review Output Dataset from K-M Survival Analysis for Surgical Failure';
309 run;
310
311 data failresultCIs;
312     set failresults;
313
314     /* create failure estimates (rather than survival)*/
315     failure = 1 - survival;
316     failureLCL = 1 - SDF_UCL;
317     failureUCL = 1 - SDF_LCL;
318
319     /* limit to records where the survival estimate has changed
320        (i.e. records where the CI is not null) */
321
322     if SDF_LCL NE . then output;
323
324     label failure = 'Cum. probability of surgical failure';
325     label failureLCL = 'Lower limit of CI for surgical failure';
326     label failureUCL = 'Upper limit of CI for surgical failure ';
327
328 run;
329
330 %sort (failresults, trtgroup);
331 proc print data = failresultCIs;
332     by trtgroup;
333     title2'Review Output Dataset from K-M Survival Analysis for Surgical Failure';
334 run;

```

- 336
- 337 **9.** Compare cumulative probability of surgical failure by 3 years for each treatment group using
- 338 a Z-test code
- 339

340 See below—combined with step #10.

341 **10. Calculate the treatment group difference (and 95% CI) in the cumulative probability of**
342 **surgical failure by 3 years.**

```
343 /* Manually enter cumulative probabilities and standard error from K-M into short
344 program to calculate Z-score, its corresponding P value, the treatment group
345 difference and 95% CI */
346
347 data check;
348     input probblr seblr probrr serr;
349     datalines;
350     0.4594 0.0518 0.3731 0.0520
351 ;
352 run;
353
354 data check;
355     set check;
356     diff = probblr - probrr;
357     sumofsquaredse = sqrt (seblr**2+serr**2);
358     cilower = diff - (1.96*sumofsquaredse);
359     ciupper = diff + (1.96*sumofsquaredse);
360     zscore = diff/sumofsquaredse;
361     pvalue = 2*(1 - probnorm(zscore));
362 run;
363
364 proc print data = check noobs;
365     var analysis probblr seblr probrr serr sumofsquaredse diff cilower ciupper zscore
366     pvalue;
367     title'Calculate CIs and P values;
368 run;
369
370
371
372 Datasets used: MASKEDEXAMS, BASELINE, ROSTER, tblIXT1Treatused (SQL)
```

373 **Objective #3: Compare the binomial proportion of surgical failure AT 3 years between**
374 **BLR and R/R treatment groups**

- 375
- 376 1. Define the outcome
 - 377 2. Determine whether exotropia failure criterion was met at the 3-year masked exam
 - 378 3. Determine whether constant esotropia failure criterion at the 3-year masked exam
 - 379 4. Determine whether stereoacuity failure criterion was met at the 3-year masked exam
 - 380 5. Determine whether patient was reoperated or underwent treatment with botulinum toxin,
381 regardless of whether he/she first met one of the three surgical failure criteria
 - 382 6. Create surgical failure at 3 years
 - 383 7. Calculate binomial proportion, treatment group difference, and 95% exact confidence
384 intervals
- 385

386 **Technical plan**

- 387 1. Define the outcome
- 388 • The secondary outcome of surgical failure AT 3 years (not BY 3 years) is defined as
389 follows:

390 **Failure** = ANY of the following criteria are met atthe3-yearmaskedexam:

- 392 1. **Exotropia** at distance OR near at any time during the exam (i.e., can be constant or
393 intermittent; determined by a cover/uncover test) with a magnitude of atleast 10 PD by
394 SPCT, confirmed by a retest
 - 395 2. **Constant esotropia** at distance OR near (determined by at least 3 cover/uncover tests—
396 one must be before any dissociation) with a magnitude of atleast 6 PD by SPCT,
397 confirmed by a retest
 - 398 3. Decrease in Preschool Randot near **stereoacuity** atleast 2 octaves (atleast 0.6 log arcsec)
399 (*see Table 3*) from the enrollment measurement, or to nil, confirmed by a retest (*see*
400 *Table 1* from objective #2)
- 401

402 Patients will also be considered a surgical failure at 3 years if they undergo **reoperation** or
403 treatment with botulinum toxin at any time during the study.

404

405 The outcome is assessed only in patients who complete the 3-year visit. To prevent biasing the
406 estimates, patients who were reoperated before being lost to follow up will not contribute to the
407 analysis (even though their surgical failure at 3 years status would have been permanently set
408 when they were reoperated, if had they completed the 3-year visit).

- 409
 - 410 2. Determine whether exotropia failure criterion was met at the 3-year masked exam
 - 411 • Created as part of objective #2 -- get data from 3-year visit record from
412 MASKEDEXAMS dataset.
 - 413
 - 414 3. Determine whether constant esotropia failure criterion at the 3-year masked exam
 - 415 • Created as part of objective #2 -- get data from 3-year visit record from
416 MASKEDEXAMS dataset.
- 417

- 418 4. Determine whether stereoacuity failure criterion was met at the 3-year masked exam
419 • Created as part of objective #2 -- get data from 3-year visit record from
420 MASKEDEXAMS dataset.
421
- 422 5. Determine whether patient was reoperated or underwent treatment with botulinum toxin,
423 regardless of whether he/she first met one of the three surgical failure criteria
424 • Use patient-level reoperation flag and reoperation date created for objective #2.
425
- 426 6. Create surgical failure at 3 years
427 • For patients who completed the 3-year visit:
428 ○ Code as 1 if any of the three surgical failure criteria are met at 3 years or if
429 reoperation occurred at any time.
430 ○ Otherwise code as 0
431
- 432 7. Calculate binomial proportion for each treatment and compare between treatment groups
433 with a Fisher's exact test. Calculate treatment group difference, and 95% exact confidence
434 intervals.
435

```
436 proc freq data = roster;  
437     tables trtgroup*failat36;  
438     exact fisher riskdiff;  
439     where vis_36 = 'Completed';  
440     title1 'Comparison of Crude % with Failure ***AT*** 3 Years';  
441 run;
```

442 **Datasets used: MASKEDEXAMS, ROSTER**

443 **Objective #4: Compare the binomial proportion with reoperation by 3 years between BLR**
444 **and R/R treatment groups**
445

- 446 1. Define the outcome
- 447 2. Determine whether patient was reoperated or underwent treatment with botulinum toxin,
448 regardless of whether patient first met one of the three surgical failure criteria
- 449 3. Get cumulative probability of reoperation by 3 years for each treatment group – from K-M
- 450 4. Compare cumulative probability of reoperation by 3 years for each treatment group using
451 two-sided Z-test
- 452 5. Calculate the treatment group difference (and 95% CI) in the cumulative probability of
453 reoperation by 3 years.
454

455 **Technical Plan**

- 456 1. Define the outcome
457
458
459 Reoperation or botulinum toxin treatment at any time during the study, including cases where
460 reoperation was completed after surgical failure was met and cases where reoperation occurred
461 without surgical failure first having been met (i.e. against protocol).

- 462 2. Determine whether patient was reoperated or underwent treatment with botulinum toxin,
463 regardless of whether he/she first met one of the three surgical failure criteria
464 • Use reoperation outcome and time to reoperation variables created for objective #2.
465
- 466 3. Get cumulative probability of reoperation by 3 years for each treatment group – from K-M
- 467 4. Compare cumulative probability of reoperation by 3 years for each treatment group using Z-
468 test
- 469 5. Calculate the treatment group difference (and 95% CI) in the cumulative probability of
470 reoperation by 3 years.
471

472 Repeat steps #8 - #10 for objective #1 using the reoperation outcome and time to reoperation
473 variables.
474

475 **Objective #5: Compare 3-year control and PACT values between BLR and R/R treatment**
476 **groups**

- 477
- 478 1. Define the outcomes
 - 479 2. Define the cohort
 - 480 3. Compare mean 3-year outcomes between treatment groups

481
482 **Technical Plan**

- 483 1. Define outcomes.
- 484 a. PACT size (distance and near)
 - 485 • Code according to size and type
 - 486 ○ Exodeviations will be coded as positive values (same as in database)
 - 487 ○ Esodeviations will be changed to negative values
 - 488
 - 489 b. Exotropia Control (distance and near)
 - 490 ○ For both distance and near, create numeric values for exotropia control where ‘not
 - 491 applicable’ will be assigned a score of 0, the same as the score for a pure phoria.
 - 492 Note that ‘not applicable’ was entered on the form when no exodeviation was present.
 - 493
 - 494

Table #1: Intermittent Exotropia Control Scale Scoring

5	Constant Exotropia
4	Exotropia > 50% of the 30-second period before dissociation
3	Exotropia < 50% of the 30-second period before dissociation
2	No exotropia unless dissociated, recovers in >5 seconds
1	No exotropia unless dissociated, recovers in 1-5 seconds
0	No exotropia unless dissociated, recovers in <1 second (phoria)
Not applicable	No exodeviation present

[figure not shown]
[figure not shown]
495
496 For both PACT and control outcomes, use the 3-year visit data for all patients who completed
497 the 3-year visit, regardless of what treatment(s) were received or if the patient had undergone
498 reoperation.

- 499
- 500 2. Limit the analysis to patients who completed the 3-year visit.
 - 501
 - 502 3. Compare mean 3-year outcome between treatment groups using ANCOVA model.

```
503 proc genmod data = roster;  
504 class trtgroup;  
505 model controlnumdi_36 = trtgroup controlnumdi_0;  
506 where comp_36 = 1;  
507 title 'Comparison of 3-year distance control between treatment groups';  
508 run;  
509
```

510 **Datasets used: MASKEDEXAMS, ROSTER**

511 **Version History**

Version Number	Author	Approver	Effective Date	Revision Description
1.0	[name]	[name] 	1-19-17	Original SAP for outcome data included in submitted AAPOS abstract (note that the analyses were specified in the protocol).
1.1	[name]	[name] 	3-1-17	For the purpose of the AAPOS presentation, added section 1.8 on secondary analyses of 3-year exotropia control and 3-year angle magnitude (note that these analyses were specified in the protocol).

512

1
2
3
4
5
6
7
8
9
10
11
12
13
14
15
16
17
18
19
20
21

IXT1 Primary Manuscript on Basic Primary Cohort

Statistical Analysis Plan for Secondary Outcomes Not Covered in Previous Analysis Plans

May 30, 2018

Revision History

VERSION NUMBER		AUTHOR	APPROVER	EFFECTIVE DATE	REVISION DESCRIPTION (INCLUDING SECTIONS REVISED)
SAP	Protocol				
1.0	5.0 6-21-17	[name]	[name]	5/14/18	Initial version
1.1	5.0 6-21-17	[name]	[name]	6/11/18	In the SAS code on line 425 that creates a p value using a z-score, changed to using the absolute value of the z score (instead of the z score itself) to account for situations in which a two-sided test yields a negative z-score.

22 **Important Notes:**

23 The primary analysis and many of the secondary analyses were completed for several abstracts and
24 presentations preceding completion of the primary manuscript. Below is a list of outcomes which are
25 documented in previous analysis plans plus outcomes which are covered herein.

26 **AAPOS Abstract and Presentation 2017**

- 27 • **Surgical failure by 3 years (primary outcome) (reabeled “suboptimal surgical outcome” at 3**
- 28 **years)**
- 29 • **Surgical failure at 3 years (reabeled “suboptimal surgical outcome” at 3 years)**
- 30 • **Reoperation by 3 years**
- 31 • **3-year PACT magnitude (distance and near)**
- 32 • **3-year control (distance and near)**

33

34 Not that the above variables were originally documented and created at the time of the AAPOS
35 presentation using pre-closeout data in January 2017; however, as part of the verification of the ESA 2017
36 presentation in August 2017, these variables were rerun using post-closeout data and incorporated into the
37 ROSTER dataset used for ESA. The manuscript dataset will start with ESA dataset and add additional
38 data needed for the manuscript.

39 **The current document contains the following outcomes:**

- 40 • **Exotropia failure by 3 years (using exotropia criteria of surgical failure)**
- 41 • **Constant esotropia failure outcome (using constant esotropia criteria of surgical failure)**
- 42 • **Stereoacuity failure outcome (using stereoacuity loss criteria of surgical failure)**
- 43 • **3-year stereoacuity (distance and near)**
- 44 • **Complete or near-complete resolution at 3 years without regard to previous surgical failure**
- 45 **(post hoc)**
- 46 • **Complete or near-complete resolution at 3 years with no previous surgical failure (pre-**
- 47 **specified)**
- 48 • **IXT Questionnaire (IXTQ) scores for parent, proxy and child components**
- 49 • **Additional tabulations**

50

51

52

53 **1.1 Objective**

54 To compare 3-year outcomes between patients treated with bilateral lateral rectus muscle recession (BLR)
55 versus those treated with unilateral lateral rectus recession (R/R)

56
57 **1.2 Cohort of Interest**

58 Briefly, the IXT1 study enrolled patients who were 3 to <11 years of age, had stereoacuity of 400 arcsec
59 or better, and were undergoing surgery for intermittent exotropia (N = 265 overall). The cohort of interest
60 is the primary cohort of 197 patients with basic-type IXT and with largest preoperative exodeviation
61 between 15 and 40 PD by PACT at remote distance, distance, or near (101 in BLR group, 96 in R/R
62 group).

63
64 **1.3 Cause-specific surgical failure outcomes**

65 As secondary analyses, three cause-specific suboptimal outcomes by 3 years were specified post hoc, for
66 the exotropia, constant esotropia, and stereo loss criteria defined in the primary outcome (Table 1). These
67 cause-specific outcomes differ from the primary outcome in two ways: 1) the primary outcome refers to
68 the first occurrence of *any* suboptimal outcome criterion (or re-operation) being met, whereas the cause-
69 specific outcomes refer to the first occurrence of the *particular* suboptimal outcome criterion being met,
70 and 2) reoperation prior to meeting a particular suboptimal outcome criteria was considered an *suboptimal*
71 *outcome* for the primary analysis but was censored as a *non-outcome* in the analysis that evaluated cause-
72 specific outcomes. For each of the three cause-specific outcomes, participants who met criteria *other than*
73 *the particular criteria being assessed* remained “at risk” for the criterion of interest unless they underwent
74 reoperation. For example, participants who met the stereo loss outcome remained “at risk” for the
75 exotropia and constant esotropia outcomes until they either met them or underwent reoperation. The
76 cumulative probability of each cause-specific outcome by 3 years and a 95% CI were obtained using the
77 K-M method. It is acknowledged that the three cause-specific outcomes are not independent because
78 reoperation is a competing risk for each (e.g., participants who met the exotropia outcome and underwent
79 reoperation were no longer at risk for meeting stereo loss or constant esotropia outcomes).

80
81 The cumulative probability (and 95% confidence interval) of each cause-specific outcome will be
82 determined using Kaplan-Meier method.

83
84 **Table 1: Three Objective Criteria for Surgical Failure**

Based on a masked exam occurring between 6 months and 3 years after randomization:

1. **Exotropia** at distance OR near at any time during the exam (i.e., can be constant or intermittent; determined by a cover/uncover test) with a magnitude of atleast 10 PD by SPCT, confirmed by a retest
2. **Constant esotropia** at distance OR near (determined by at least 3 cover/uncover tests—one must be before any dissociation) with a magnitude of atleast 6 PD by SPCT, confirmed by a retest
3. Decrease in Preschool Randot near **stereoacuity** atleast 2 octaves (atleast 0.6 log arcsec) (*see Table 3*) from the enrollment measurement, or to nil, confirmed by a retest

Baseline stereoacuity at enrollment, in arcsec	Level needed at follow up visit to meet surgical failure criteria, in arcsec
40"	200" or worse
60"	400" or worse
100"	400" or worse
200"	800" or worse
400"	Nil

Note that reoperation without having met any of the three objective criteria was also considered a surgical failure in the primary analysis.

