1184 • If visual acuity is found to be reduced by 0.2 logMAR from the previous visit and the
1185 patient is wearing a Fresnel prism, visual acuity should be retested in trial frames.
1186 • If visual acuity is found to be reduced by 0.2 logMAR or more (2 lines or 10 letters)
1187 from the previous visit (after removal of Fresnel prism if applicable), a cycloplegic
1188 refraction must be performed and visual acuity retested in current refractive
1189 correction based on the cycloplegic refraction.
- 1190 7. Cycloplegic refraction if not performed within the last 12 months
1191 ○ Management of refractive error is subject to the guidelines in *section 5.3*.

1192
1193 In addition, the following will be recorded:

- 1194 • Any nonsurgical treatment of exotropia, esotropia or symptomatic diplopia (e.g., prism)
1195 • Any treatment of amblyopia [interocular visual acuity difference of more than 0.2
1196 logMAR (2 lines on ATS HOTV or 10 letters on E-ETDRS) and worse eye acuity of
1197 worse than 0.3 logMAR (20/40 on ATS HOTV or 70 letters on E-ETDRS)]
1198 • Any change in refractive correction
1199

1200 Treatment can be prescribed as follows:

- 1201 • Nonsurgical treatment of any overcorrection, undercorrection, or deviations associated
- 1202 with diplopia is at investigator discretion.
- 1203 • If any of the surgical failure criteria are met (*section 4.5.1*), the investigator may elect to
- 1204 reoperate (*section 4.7*). If none of the surgical failure criteria are met, the investigator
- 1205 should not reoperate.

1206
 1207 All patients should continue in follow up through 3-years, regardless of whether they undergo
 1208 reoperation.
 1209

1210 **4.5.1 Surgical Failure Criteria**

1211 Patients will be considered a surgical failure if at any visit occurring 6 months or later any of the
 1212 following failure criteria are present by masked examiner testing (*section 4.5.2*)*:

- 1213 1. Exotropia at distance OR near at any time during the exam (i.e., can be constant or
- 1214 intermittent; determined by a cover/uncover test) with a magnitude of at least 10 PD by
- 1215 SPCT, confirmed by a retest
- 1216 2. Constant esotropia at distance OR near (determined by at least 3 cover/uncover tests—one
- 1217 must be before any dissociation) with a magnitude of at least 6 PD by SPCT, confirmed by a
- 1218 retest
- 1219 3. Decrease in Preschool Randot near stereoacuity at least 2 octaves (at least 0.6 log arcsec) (*see*

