**Bilateral Lateral Rectus Recession Versus Unilateral Recession-
Resect for Intermittent Exotropia**

Statistical Analysis Plan / Technical Plan

March 1, 2017

Version 1.1

1 **IXT1 Three-Year Analysis**

2
3 **1.1 Objective**

4 To compare 3-year outcomes between patients treated with bilateral lateral rectus muscle
5 recession (BLR) versus those treated with unilateral lateral rectus recession (R/R)

6
7 **1.2 Cohort of Interest**

8 197 patients with basic-type IXT with largest preoperative exodeviation between 15 and 40 PD
9 by PACT at remote distance, distance, or near (101 in BLR group, 96 in R/R group).

10
11 **1.3 Primary Outcome – Surgical Failure by 3 Years**

12 The primary outcome of surgical failure by 3 years is defined as follows:

13
14 **Failure** = ANY of the following criteria are met at masked exam occurring between 6 months
15 and 3 years after randomization:

- 16 1. **Exotropia** at distance OR near at any time during the exam (i.e., can be constant or
17 intermittent; determined by a cover/uncover test) with a magnitude of atleast 10 PD by
18 SPCT, confirmed by a retest
- 19 2. **Constant esotropia** at distance OR near (determined by at least 3 cover/uncover tests—
20 one must be before any dissociation) with a magnitude of atleast 6 PD by SPCT,
21 confirmed by a retest
- 22 3. Decrease in Preschool Randot near **stereoacuity** atleast 2 octaves (atleast 0.6 log arcsec)
23 (*see Table 3*) from the enrollment measurement, or to nil, confirmed by a retest

24
25 **Table 1: Preschool Randot Stereotest**

Baseline stereoacuity at enrollment, in arcsec	Level needed at follow up visit to meet surgical failure criteria, in arcsec
40"	200" or worse
60"	400" or worse
100"	400" or worse
200"	800" or worse
400"	Nil

26
27 Patients will also be considered a surgical failure for analysis if they undergo **reoperation** or
28 treatment with botulinum toxin at any time during the study.

29
30 **1.4 Primary Analysis**

31 The cumulative proportion of patients meeting criteria for failure by 3 years will be obtained
32 using the Kaplan-Meier method and compared between treatment groups using the Z test. This
33 will allow patients who drop out prior to 3 years to contribute to the estimation of the proportion
34 of surgical failure at 3 years. In this analysis, all patients who meet surgical failure criteria prior
35 to 3 years will be counted as failures at the first visit at which surgical failure criteria are met.

36

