- 218 • Create a numeric variable for SPCT magnitude by setting '>50' equal to a nonsense
219 value of 888. *Note that no means will be calculated on this variable.*
- 220 • Exotropia failure criteria is met if the masked exam shows the patient has an exotropia
221 of 10 or greater at distance or near by SPCT, confirmed by a retest. If the worsening
222 was not confirmed by the retest or the retest was not completed, the patient was
223 considered not to have met exotropia failure criteria. Requires the following:
 - 224 ○ SPCT of ≥ 10 PD at distance or near on initial testing and retesting
 - 225 ○ Tropia type = 'Exo' at distance or near on initial testing and retesting
 - 226 ○ Note that corresponding size and type must meet above criteria for the same
227 distance for initial and retest.
- 228 • *Unlike IXT2, the exotropia does not need to be constant to meet criteria and does not*
229 *need to occur at both distance and near.*

230

231 4. Determine whether constant esotropia failure criteria were met for each masked exam

- 232 • Evaluate all masked exams. *Even though only the first masked exam where failure*
233 *criteria is met is relevant to the primary outcome, save constant esotropia failure criteria*
234 *flag in a masked-exam-level dataset because interested in whether this criteria is met at*
235 *the 3 year visit also, and may also be interested in other visits as well.*
- 236 • For each masked exam, determine whether constant esotropia failure criterion was met.
- 237 • Use SPCT variables created above.

- 238
- 239
- 240
- 241
- 242
- 243
- 244
- 245
- 246
- 247
- Constant esotropia failure criterion is met if the masked exam shows the patient has an esotropia of 6 or greater at distance *or* near (throughout exam) by SPCT, confirmed by a retest. If the worsening was not confirmed by the retest or the retest was not completed, the patient was considered not to have met constant esotropia failure criteria. Requires the following:
 - SPCT of ≥ 6 PD at distance and at near on initial testing and retesting
 - Tropia type = ‘Eso’ at distance and at near on initial testing and retesting
 - Assessment of esodeviation throughout exam = ‘Constant esotropia’ at time of initial testing and at time of retesting
- 248
5. Determine whether stereoacuity failure was met for each masked exam
- 249

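### The SAP's programming rule for constant-esotropia failure requires both test distances, but the endpoint it implements needs only one

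*SAP*

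**What the plan says.** Protocol 4.5.1 defines failure criterion 2 as "Constant esotropia at distance OR near (determined by at least 3 cover/uncover tests", with at least 6 PD by SPCT and confirmation on retest. Protocol 6.1.1 and the flow chart in 1.4 give the same either-distance rule. So do the March 2017 SAP (section 1.3, Objective #2 step 1, Objective #3 step 1) and the 2018 SAP (Table 1 in section 1.3, Objective #2 step 1). Section 1.3 of the March 2017 SAP words it "at distance OR near (determined by at least 3 cover/uncover tests".

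Step 4 of the Objective #2 technical plan in the March 2017 SAP turns this criterion into a flag for each masked exam. Its lead sentence keeps the either-distance rule: "esotropia of 6 or greater at distance *or* near (throughout exam) by SPCT". Three requirements follow. The first two, SPCT of at least 6 PD and tropia type Eso, must each hold "at distance and at near on initial testing and retesting". The third relies on one exam-level field, "Assessment of esodeviation throughout exam", which must equal constant esotropia at both the initial test and the retest.

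Step 3, the parallel exotropia rule, uses *or* in both its lead sentence and its requirements. It then adds a matching condition: "Note that corresponding size and type must meet above criteria for the same" distance at initial test and retest. Step 4 has no such condition.

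**The concern.** The list of requirements is the part a programmer codes from. Followed literally, it is a narrower endpoint than the one the protocol defines. It can leave the number of failures unchanged or lower it, but it cannot raise it.

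The flag enters the primary outcome directly: step 7 takes the first masked exam "at which any of the three objective failure criteria were met" as the failure visit. An error would also carry into:

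- failure AT 3 years (Objective #3), which reuses the flag: "Created as part of objective #2 -- get data from 3-year visit record from" the masked-exam dataset;
- the cause-specific esotropia outcome in the 2018 SAP (Objective #2), which starts from that same dataset and censors at reoperation, so reoperation cannot rescue a missed case there;
- the no-previous-failure version of resolution (2018 SAP, Objective #4), through failure by 3 years;
- the esotropia tabulations (2018 SAP, 1.7 and 1.8);
- the check on whether reoperation depends on treatment group (March 2017 SAP, 1.6 and 1.7), which is restricted to children who met failure criteria. A child who qualified at one distance and was then reoperated could drop out of that check and appear to have been reoperated against protocol.

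The post hoc resolution outcome that ignores earlier failure is not affected, because it separately requires esotropia below 6 PD at both distances.

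**Working it through.** **1. Is there a reading that removes the conflict?**

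- *Shorthand for testing both distances.* Unlikely, because step 3 writes *or* in its requirements and adds a matching condition for the single qualifying distance.
- *The third requirement restores the either-distance rule.* It does not. It is a single exam-wide field, and the SAP does not say how it applies when only one distance qualifies.
- *A both-distances rule elsewhere in the protocol.* Section 4.4.1 has one, for prism management at 8 weeks. That is a separate rule: the flow chart in 1.4 keeps both distances for prism and either distance for failure.
- *Fit with the outcome categories in protocol 6.1.1.* Take constant esotropia of 8 PD at near and 0 at distance. Success needs esotropia below 6 PD at both distances, and the esodeviation item under indeterminate covers only intermittent esotropia or esophoria. Under a both-distances failure rule this child would fit no category, unless an exodeviation item, the stereoacuity criterion or reoperation applied.

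**2. Which children are classified differently** (constant esotropia, confirmed on retest)

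| Distance / near, PD | Endpoint definition (either) | Step 4 as listed (both) |
|---|---|---|
| 8 / 8 | failure | failure |
| 8 / 0 or 0 / 8 | failure | not failure |
| 8 / 4 or 4 / 8 | failure | not failure |
| 4 / 4 | not failure | not failure |

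**3. Size, as an illustration only.** The inputs are the K-M values typed into the March 2017 SAP (Objective #2, step 10): BLR 0.4594 (SE 0.0518) and R/R 0.3731 (SE 0.0520). These are pre-closeout; the 2018 SAP states that the outcomes were rerun on post-closeout data.

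The SAP's own Z test gives:

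- difference = 0.4594 − 0.3731 = 0.0863
- SE = √(0.0518² + 0.0520²) = 0.0734
- z = 0.0863 / 0.0734 = 1.176, p = 0.24
- 95% CI −0.058 to 0.230

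The effective sample size implied by each SE is n = p(1 − p)/SE²:

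- BLR: 0.4594 × 0.5406 / 0.0518² = 92.6, so one case is worth 1.08 points
- R/R: 0.3731 × 0.6269 / 0.0520² = 86.5, so one case is worth 1.16 points

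Restoring k assumed missed failures, with each SE recomputed as √(p(1 − p)/n):

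| Assumed missed cases | BLR − R/R, points | p |
|---|---|---|
| none | 8.63 | 0.24 |
| R/R 1 | 7.47 | 0.31 |
| R/R 3 | 5.16 | 0.49 |
| R/R 5 | 2.85 | 0.70 |
| R/R 8 | −0.62 | 0.93 |
| BLR 4 | 12.95 | 0.078 |
| BLR 5 | 14.03 | 0.056 |
| BLR 6 | 15.11 (95% CI 0.7 to 29.5) | 0.040 |
| 5 in each arm | 8.25 | 0.27 |
| BLR 1 and R/R 3 | 6.24 | 0.40 |

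Scaling by the numbers randomised (96 and 101) gives the same pattern: eight in R/R give 0.3 points (p=0.97), and six in BLR give 14.6 points (p=0.047). This is a binomial approximation to the K-M estimates, and every case count is assumed.

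**The case against.** The strongest reply is that the governing definition is not in doubt and that two sub-bullets are probably a drafting slip. Step 3 contrasts itself with IXT2, so adapted wording is plausible, though that is inference. The 2018 SAP also calls the masked-exam dataset verified. This bears on what was probably run, but it does not settle it: the documents do not say which rule the dataset was verified against.

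Four narrower points stand in whole or in part.

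- **Timing.** The primary test compares cumulative failure at 3 years. A case still captured by then matters only through intervening censoring, and later capture can raise the estimate. With 10 children and 2 censored at 18 months, one failure at 6 months gives 10%; the same failure at 30 months gives 1/8 = 12.5%. The statement that failures can only fall applies to the count, not to every K-M estimate.
- **Direction.** Protocol 6.6 expects R&R to fail mainly through consecutive esotropia, which suggests that an undercount would favour R/R. But that passage concerns esotropia that prism cannot manage. Those children are among the likelier to be reoperated, and so counted anyway. It says nothing about one-distance esotropia.
- **Number affected.** If the exam-wide field means manifest throughout the exam (protocol 2.5), the affected children may be mainly those esotropic at both distances but below 6 PD at one. Some may also meet the stereoacuity criterion.
- **Significance.** No R/R-only scenario above reaches p<0.05. The one that does needs six cases in BLR and none in R/R, against the protocol's expectation.

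These points limit the likely effect. They do not reconcile the text.

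**Conclusion.** The concern holds. Step 4 contradicts its own lead sentence and every definition of the endpoint, and nothing else in the documents corrects it. It is a wrong rule for a primary-endpoint component, not a missing detail, so the text needs correcting whichever rule was run.

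The effect on results cannot be determined. It depends on whether the both-distances rule was executed, and on how many children had confirmed constant esotropia reaching 6 PD at one distance only and were not captured by another route. If the either-distance rule was run, or there are no such children, the effect is nil. Otherwise each missed child is worth about 1.1 points on the pre-closeout estimates. The a priori expectation is an overstated R/R advantage, and the assumed R/R-only scenarios do not change significance. The actual direction is unknown.

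**What to change.** 1. **Check the executed code first.** Establish which rule built the esotropia flag in MASKEDEXAMS. Report by arm the number of children with confirmed constant esotropia reaching 6 PD at one distance only. Of these, state how many are already failures by another route and how many would change only in failure time.
2. **Correct the text in a dated revision that records what was run.** Rewrite the two bullets as SPCT of at least 6 PD and type Eso at distance or near, with size and type matched at the same distance on initial test and retest, as in step 3. State how the single throughout-exam field applies when only one distance qualifies.
3. **Rerun only if the both-distances rule was used.** Rebuild the flag on post-closeout data. Repeat the primary, AT-3-years, cause-specific esotropia and no-previous-failure resolution analyses, the reoperation-by-group check, and the tabulations that use the flag. If the either-distance rule was used, the text correction is enough.

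The cost is two corrected SAP lines plus a rule for the exam-wide field, one code check and one count by arm. No new data are needed: protocol 4.5.2 already has the retest cover SPCT at both distances where the tropia can be measured.
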